# **DOUBLE-BLINDED, RANDOMIZED, CONTROLLED TRIAL TO STUDY THE EFFECT OF OMNILUX LIGHT-EMITTING DIODE ON WOUND HEALING FOLLOWING LOWER EXTREMITY SURGICAL WOUNDS LEFT TO HEAL BY SECOND INTENTION**

**Amendment #1: 12/10/12**

## **I. INTRODUCTION**

The first published data that the LED (Light Emitting Diode) light may be beneficial during wound healing occurred during the 18th century by Fubini and colleagues. Their early work on subcellular organelles was confirmed nearly 100 years later by Tina Karu demonstrating that 633 nm light targeted cytochrome c in the mitochondrial electron transport chain. Much recent research on LED has occurred largely as a result of NASA's program to develop a light source to grow plants on space shuttles. This recent research has focused on how the LED works on biological tissue and its applications to medicine.

Similar to the 633 nm light emitted by the LED, red light from the HeNe 633 nm laser has been shown to induce fibroblast monolayer formation faster with better alignment when compared to non-irradiated controls. The LED, when used in the 830 nm range, stimulates macrophages and neutrophils to perform chemotactic, phagocytic functions more quickly. It also increases fibroblast release of fibroblast growth factor by nearly 30 times. Perhaps most intriguingly, 633 nm and 830 nm LED light has been shown to stimulate keratinocytes to release a large amount of cytokines, and migrate into the dermis to aid in the dermal wound healing process. These photoactivated keratinocytes improve the cellularity and epidermal organization especially in the stratum corneum.

The 830/633 nm LED has been used to improve wound healing after an Er:YAG/CO2 ablative laser system treatment. The experimental group received the 830/630 nm LED following ablative laser therapy while the control group received only the 630 nm LED after ablative laser treatment. The mean healing time for the experimental group was 6 weeks versus 13 weeks for the control group. Similarly, another study measured healing time after upper blepharoplasty and found healing time to be reduced one-half to one third in the 830/633 nm group. Another study using the LED (830/633 nm) treatment after Er:YAG laser ablation of deep plantar warts reduced the healing time by nearly half and reduced post-operative pain by 10% involving 121 subjects. Lower extremity ulcers have also been shown to be benefitted in terms of healing times by the 830 nm LED in a pilot study.

Wounds on the lower extremity heal more slowly than wounds on the head and neck and can remain deep red or violaceous for six months to one year. The decision to allow lower extremity wounds to heal by second intention is guided by a difficulty in using primary closure in many lower extremity wounds because of excess wound tension and limited tissue mobility. Decreased tissue laxity creates increased wound tension and an increased likelihood for wound dehiscence. By using second intention as a method for surgical defect management the physician

need not worry about dehiscence and retained suture material serving as a nidus for infection. Wound management is simple, requiring only a bandage and daily care that can be done at home by the patient, family, or visiting nurse. A major limitation of allowing surgical defects on the lower extremity to heal by second intention is the long healing time that can often take months. For this reason, modalities that can hasten this process are in demand.

## **II. OBJECTIVE**

The goal of the study is to evaluate the efficacy of the light-emitting diode in the treatment of lower extremity surgical wounds left to heal by secondary intention by way of a double-blinded randomized, controlled study.

## **III. STUDY PLAN**

Patients will be recruited from patients at the University of Miami Miller School of Medicine Mohs/Laser Unit. On the day of surgery and wound defect creation (day 0), patients will be informed of the study, and given the option of participating. If he or she decides to participate, the patient will be randomized into one of two groups in blocks of two by coin flip. The patient will remain blinded to the outcome of randomization. The experimental group will receive treatment with the light emitting diode (LED) for one session lasting 20 minutes of exposure at an intensity of 105 mW/cm^2 for a total of 126 J/cm^2 over the wound site. The LED emits light at wavelengths of 633 nm and 830 nm at fluences of 126 and 66 J/cm^2. This study will only utilize the 633 nm wavelength. The control group will receive sham light treatment for 20 minutes with standard of care for second intention healing and no LED treatment. In this case, a sham light treatment refers to regular light (not LED) exposure for 20 minutes. The sham light comes from the same device as the treatment light (Omnilux machine) however, this light has no anticipated effects on wound healing and is used simply to reduce the amount of bias that sometimes complicates the results of these studies. There is no added risk or benefit for the patients in the control group exposed to the sham light.

On day 0 the patients will be informed of the study and randomized into one of two groups by coin flip to either the experimental or control group. The patients will be blinded to which group they have been randomized too. Group 1 is the control group, which will receive sham light treatment and standard of care for lower extremity wounds. Group 2 represents the experimental group, which will receive LED treatment plus standard of care. The experimental group will receive treatment with the light emitting diode (LED) at 633 nm at one session lasting 20 minutes of exposure at an intensity of 105 mW/cm^2 for a total of 126 J/cm^2 over the wound defect, one week after wound creation (+/- 3 days). The control group will receive no LED treatment, however they will be exposed to a sham light for the duration of 20 minutes as well as receive standard of care for their lower extremity wound. Treatment will occur at one-week intervals (+/- 3 days) for a total

of 4 treatments for both the experimental and control/sham groups. The wounds will be created as a result of Mohs micrographic surgery or surgical excision, and left to heal by secondary intention. An Aranz silhouette camera will be used with a measurement stick on the picture. Changes from the baseline wound (including length and width) will be measured along with wound depth. These two parameters will be compared at the 1 week, 2 week 3 week, and 4-week treatment (or sham treatment) visits. After the 4th and final treatment with the LED or sham light, the patients will be followed at 1-week intervals (+/- 3 days) until the wound has closed or for a maximum of 3 months, whichever occurs first. Once the wound has closed, patients will be evaluated a final time, 1 week after wound closure to ensure that complete wound healing has indeed occurred. After this final wound evaluation, the patient's commitment required for this study will end and regular follow-up with dermatology will resume outside the scope of this study.

The clinical photographs taken before and after either LED or sham light treatment at each study visit will be evaluated by blinded assessor(s) who are board-certified dermatologist(s).

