#### **IV. SUBJECT POPULATION**

##### **A. Number of Subjects**

We plan to prospectively enroll 40 patients in this study.

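### Coin-flip allocation in blocks of two fixes the second assignment of each pair, and nothing in the protocol hides earlier assignments from enrolling staff

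*Combined protocol and SAP*

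**What the plan says.** The protocol describes allocation twice in section III (Study Plan). The first paragraph says that after agreeing to take part "the patient will be randomized into one of two groups in blocks of two by coin flip". The second says that patients are "randomized into one of two groups by coin flip to either the experimental or control group", on day 0, and does not mention blocks.

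Section IV.A gives the size: "We plan to prospectively enroll 40 patients in this study". Recruitment is at one unit, and no stratification is mentioned.

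On blinding, section III says "The patient will remain blinded to the outcome of randomization", and later that the photographs go to blinded dermatologist assessors. The protocol does not say who flips the coin, who enrols, who operates the device, or whether these are different people. It mentions no prepared list, envelopes or central allocation. Section V has the assigned group recorded prospectively but does not say who holds that record.

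**The concern.** A block of two is the most predictable permuted block there is: once the first assignment is known, so is the second. That matters only if the person deciding whom to invite can learn the first, and the protocol puts no barrier in the way. Invitation and consent take place on day 0, when the wound already exists and can be seen. Section IV.B admits any wound up to 5 cm x 5 cm with no minimum, so there is room for discretion over whom to approach. Staff who expected LED next could favour patients likely to heal well, and the reverse when they expected sham.

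A coin flipped on site also leaves no pre-specified sequence against which the recorded groups could be checked. In addition, the two paragraphs can be read as two different procedures with different properties.

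**Working it through.** **Inputs.** N = 40 (section IV.A). Two arms, block size 2 (section III, first paragraph). The 1:1 ratio is implied by these. One unit, so one running sequence. The documents give no alpha, SD or effect size and no figure for predictability, so there is no plan figure to reproduce.

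**Step 1: predictability under blocks of two.**
- Blocks: 40 / 2 = 20.
- Determined assignments: one per block, so 20 of 40 = 50%.
- Expected correct guesses per block when earlier assignments are known: 0.5 + 1 = 1.5 of 2 = 75%, or 30 of 40.

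**Step 2: alternatives, for a guesser who knows the earlier assignments.**

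| Method | Determined, of 40 | Correct guesses, of 40 |
|---|---|---|
| Fixed blocks of 2 | 20.0 (50%) | 30.0 (75%) |
| Fixed blocks of 4 | 13.3 (33%) | 28.3 (71%) |
| Varying blocks of 4 and 6, sizes undisclosed* | about 0.4 (1%) | 27.6 (69%) |
| One permuted 20:20 list | 40/21 = 1.9 (5%) | 23.5 (59%) |
| Independent coin flips | 0 | 20 (50%) |

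*By simulation; the guesser uses only the running imbalance. The other rows are exact.

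**Step 3: independent flips (one reading of the second paragraph).** With X ~ Binomial(40, 0.5), P(X = 20) = 12.5% and P(|X − 20| ≥ 5) = 15.4%, the chance of 25:15 or worse. The precision cost of a 25:15 split is small: sqrt(1/25 + 1/15) / sqrt(1/20 + 1/20) = 0.327 / 0.316 = 1.03, a 3% larger standard error.

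**Step 4: what selection could do (illustration only).** Assume no treatment effect, SD 1, 20 per arm, and a two-sided 5% unadjusted t test on 38 df (critical value 2.024, SE = sqrt(2/20) = 0.316). Let η be the shift in prognosis, in SD, of a patient enrolled into a known slot. Let k be the number of LED patients who are second in their pair, so that 20 − k control patients are.

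- *Both directions* (known-LED patients better by η, known-control patients worse by η): the arm difference is ηk/20 + η(20 − k)/20 = η, whatever k is. At η = 0.25 the noncentrality is 0.25 / 0.316 = 0.79 and rejection is 12.0%. At η = 0.5 it is 1.58 and rejection is 33.8%. Simulating the paired sequence itself gives about 12% and 32%; the rates are slightly lower because shifting only part of each arm adds variance.
- *One direction only* (for example, only known-LED slots affected): the arm difference is ηk/20, on average η/2. Averaging the noncentral t over k ~ Binomial(20, 0.5) gives 6.8% at η = 0.25 and 12.4% at η = 0.5.

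**Step 5: would the baseline test reveal it?** Section VII suggests an unpaired t test of baseline wound size. If selection acted entirely through wound size, in both directions at 0.25 SD, that test faces the same 0.25 SD difference with the same 20 per arm. It would be significant only about 12% of the time.

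**The case against.** The strongest objection is that knowledge of the first assignment is assumed. A reader might infer that half of the 40 assignments are in fact known to enrolling staff, because the unit that enrols also runs the device. The documents do not support that. They do not say that one person enrols, flips and treats. Section III's second paragraph also places the LED session about one week after wound creation (± 3 days), so the next patient could be enrolled before the device shows anything. This stands as a limit on the claim. It does not remove it: the flip itself is on day 0, somebody sees the result, and no step keeps that result from the enroller. The label double-blinded does not fill the gap, since the blinding described covers patients and photograph assessors only.

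A reader might also infer that selection could never be corrected in analysis. That goes too far. Wound size is recorded, outcomes are changes from the baseline wound, and section VII considers ANCOVA. Adjusting for baseline size could remove selection that acts through measured size, but not through unmeasured prognosis. Section VII has not settled on ANCOVA either.

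Third, the second paragraph may only abbreviate the first. That is possible. But if it means independent flips, the predictability disappears, so the text has to say which procedure applies. The imbalance that independent flips allow costs little precision and would not be a serious flaw alone.

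Finally, the shift sizes in step 4 have no source in the protocol. This is correct: they are illustrative, and the larger rates need selection in both directions.

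**Conclusion.** The point holds in conditional form. As written in the first paragraph of section III, the rule makes 20 of 40 assignments (50%) a function of the preceding one, with 75% correct guesses for anyone who knows the earlier assignments. These figures rest only on the block size, two arms and N = 40. That enrolling staff would know the earlier assignments is neither stated nor prevented, so selective enrolment is possible and not demonstrated.

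The amount of bias cannot be derived from the documents. Under an unadjusted 5% t test, assumed shifts of 0.25 SD and 0.5 SD on the known assignments give false-positive rates of about 12% and 32–34% if selection works in both directions, and about 7% and 12% if in one only. Adjustment for baseline wound size could reduce these rates where selection acts through measured size.

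This is a flaw in a stated rule and not just missing detail. It cannot be undone once patients are allocated and is cheap to correct beforehand, so it should be fixed before enrolment. The two descriptions of the coin flip need reconciling whichever was intended.

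**What to change.** In both paragraphs of section III, replace the coin-flip wording with a single method: one computer-generated permuted list of 20 LED and 20 sham. About 2 of 40 assignments are then determined by the earlier ones. Varying blocks of 4 and 6 are a weaker choice here, because someone who knows earlier assignments would still guess about 69% correctly, against 59% with the single list.

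Have the list prepared by an existing staff member who does not enrol patients, and hold it in sequentially numbered, opaque, sealed envelopes. Open each envelope only after consent and enrolment are complete, and keep the result from enrolling staff. Keep the existing day-0 timing text; if the assignment is to be opened at the first light session instead, say so explicitly.

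The cost is a short amendment, a one-off list, 40 envelopes and some time from a staff member outside enrolment. The protocol does not say whether such a person is available, so the sponsor should confirm this. No extra patients are needed.

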##### **B. Inclusion Criteria**

Surgical defect on the lower extremity left to heal by secondary intention. There is no minimum size for the wound. Women of child-bearing potential must be using medically-accepted contraceptive measures in order to participate in the study. Patients must be able to complete all study-related visits as scheduled. Maximum size of the wound is 5cm x 5cm.

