#### **V. STUDY PROCEDURES**

Those patients who have a surgical defect on the lower extremity that will be left to heal by secondary intention and are willing to participate in the study will be consented and enrolled in the study.

The following information will be recorded in a prospective fashion: Patient's age, gender, race/ethnicity, type of skin cancer removed, clinical size of lesion (mm) and size of resulting defect following surgery. It will also be recorded to what group, treatment with LED and standard wound care versus sham light treatment and standard wound care with no LED. Clinical photos of the lesion will also be taken.

The experimental group will receive treatment with the light emitting diode (LED) for 20 minutes of exposure at an intensity of 105 mW/cm^2 for a total of 126 J/cm^2, over the wound site. The LED emits light at wavelengths of 633 nm and 830 nm at fluences of 126 and 66 J/cm^2. This study will only utilize the 633 nm wavelength. The control group will receive sham light treatment for 20 minutes duration and standard of care for second intention healing without the LED treatment. This includes maintenance of a clean and moist wound environment. Patients will keep the wound covered with an occlusive bandage and will perform daily dressing changes. Daily gentle cleansing with soap and water and the application of antibacterial ointment as needed for wound hydration will be the recommended standard of care for both treatment and control groups.

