## **VII. STATISTICAL CONSIDERATIONS**

This will depend on whether we want to measure a change between the experimental and control group at particular time intervals and between groups (ANCOVA) OR do we just want to measure the difference between the control and experimental groups at particular time periods (t test). If we just do a t test, then we will not be able to make intragroup comparisons, but it will be very easy to analyze, yet still determine if the experimental group accelerates wound healing in comparison to the control group. In addition, we should probably run an unpaired t test at baseline to make sure no statistically significant difference exists in wound

size between the experimental and control groups, otherwise it could confound our results one way or the other.

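### Starting wound size is named as a possible confounder, but no adjustment for it is fixed, and the proposed baseline t test flags only differences above about 0.64 SD

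*Combined protocol and SAP*

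**What the plan says.** All references are to the Combined protocol and SAP.

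- **Allocation (section III, Study Plan).** Enrolment is on the day of surgery: "On the day of surgery and wound defect creation (day 0), patients will be informed of the study". Then "the patient will be randomized into one of two groups in blocks of two by coin flip". The next paragraph describes patients as "randomized into one of two groups by coin flip to either the experimental or control group", with no mention of blocks. No stratification or minimisation factor is named anywhere.
- **Number (section IV.A).** "We plan to prospectively enroll 40 patients in this study".
- **Eligible size (section IV.B).** "There is no minimum size for the wound", and "Maximum size of the wound is 5cm x 5cm".
- **Size is collected (section V).** The recorded data include "size of resulting defect following surgery". No calendar day is given.
- **Analysis (section VII).** The choice between ANCOVA and a t test is left open, and no covariate is named for the ANCOVA. In tentative wording, the section suggests an unpaired t test at baseline to "make sure no statistically significant difference exists in wound" size between the arms, because such a difference might confound the result in either direction. It does not say what follows if the test is significant.

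**The concern.** The plan identifies one prognostic variable as a threat to its conclusion and collects it, but commits to nothing that deals with it. Allocation ignores size, because blocks of two equalise only the head count. The baseline test comes after allocation and can prevent nothing. With 20 per arm it would also call many appreciable differences non-significant, and a reader could take that as evidence that the arms are comparable. A plain t test, which the plan describes as the easy option, would then carry any imbalance into the estimated LED effect.

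Two things are at stake. One is precision: a trial of 40 patients gives up power if it ignores a baseline value related to the outcome. The other is how the single result is read, since an unadjusted estimate from a visibly imbalanced trial is hard to interpret in either direction.

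**Working it through.** The plan gives no alpha, power, SD or effect size, so there is no stated figure to reproduce. A two-sided 5% level is assumed throughout.

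**1. Chance of imbalance.** Inputs: 40 patients (section IV.A), 20 per arm under blocks of two (section III).
- SE of the difference in mean starting size, in SD units: √(1/20 + 1/20) = √0.1 = 0.316.
- A difference of 0.5 SD gives z = 0.5/0.316 = 1.58. P(|difference| > 0.5 SD) = 2 × (1 − Φ(1.58)) = 11.4%.
- With the observed pooled SD (t, 38 df): 12.2%.
- With a simple coin flip, the other reading of section III: 11.9%, or 12.7% with the observed SD.
- Simulation with uniform or skewed wound areas: 10.9% to 12.2%.
- If only 36 or 32 patients are analysed: 13.4% or 15.7%.

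So the figure is about 11-13% for 40 patients, counting both directions. For one named arm it is half: 11.4%/2 = 5.7%, about 1 in 18.

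**2. What the baseline t test can detect.** The critical value on 38 df is 2.024, and 2.024 × 0.316 = 0.64 SD. A difference of 0.5 SD gives p = 0.12. Since 12.2% of trials exceed 0.5 SD and 5% exceed 0.64 SD, about 7% of trials would pass the test while differing by 0.5 to 0.64 SD.

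**3. What imbalance does to an unadjusted comparison.** Assume a correlation r of 0.5 or 0.7 between starting size and outcome; the documents give none. With no LED effect and a baseline difference of exactly 0.5 SD, the expected outcome difference is r × 0.5 = 0.25 or 0.35 SD. The chance of a false positive in such a trial is about 9% or 12%. Averaged over all randomisations, it remains about 5%.

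**4. What adjustment gains.** Assume a true effect of 0.7 SD of the outcome. ANCOVA reduces the outcome SD by the factor √(1 − r²).

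| Analysis | Non-centrality | Power |
|---|---|---|
| t test | 0.7/0.316 = 2.21 | 58% |
| ANCOVA, r = 0.5 | 0.7/(0.866 × 0.316) = 2.56 | about 70% |
| ANCOVA, r = 0.7 | 0.7/(0.714 × 0.316) = 3.10 | about 85% |

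Simulated ANCOVA power, which includes the small loss from chance imbalance, is 69.5% and 84.9%.

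**5. What stratified allocation adds.** For normally distributed size split at the median, the SD of the baseline difference falls to 0.316 × √(1 − 2/π) = 0.19, so P(|difference| > 0.5 SD) is 0.9%; simulated with blocks of two in each stratum it is 1.1%. With a cut-off well below the median it is about 4%. ANCOVA power does not move: 69.5% unstratified against 69.4% stratified at r = 0.5, and 84.9% against 84.9% at r = 0.7. Stratifying narrows the spread of an unadjusted estimate by about 9-17%, but a plain t test that ignores the strata then becomes conservative, with about 2-3.5% false positives.

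**The case against.** The strongest reply is that unstratified randomisation is valid. Chance imbalance is already counted in the 5% error rate: simulated false positives without stratification are 5.2% for the t test and 4.9% for ANCOVA. Once size is a covariate, even a 0.5 SD imbalance costs little: the variance rises by (0.25/38)/0.10 = 6.6%, about 3% in SE. All of this stands, and it is why the main change belongs in the analysis rather than the allocation.

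A second reply is that section VII already mentions ANCOVA and section III measures changes from the baseline wound. This stands only in part. ANCOVA is one of two options and names no covariate, and absolute change can still depend on starting size. A t test on change would, however, recover some of the gain. If the SDs at baseline and follow-up were equal, the variance of change relative to that of follow-up size would be 2(1 − r): 1.0 at r = 0.5 and 0.6 at r = 0.7. ANCOVA gives 1 − r² = 0.75 and 0.51.

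A reader might also infer more than the documents support:
- **That the lack of size strata biases the trial.** It does not; the imbalance is random and two-sided.
- **That the range from no minimum to 5 cm x 5 cm makes imbalance more likely.** A probability in SD units does not depend on the range. A wide range only makes half an SD larger in centimetres, and the documents give no size distribution from which to say by how much.
- **That starting size is the strongest driver of healing, or passes directly into the photograph ratings.** Section VII says only that it could confound, and no rating scale is given.
- **That size is recorded on the day of randomisation.** Section V gives no day. The inference is reasonable, because surgery and randomisation share day 0 and the maximum size must be checked for eligibility.

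**Conclusion.** The point holds as a weakness of the analysis plan, with allocation secondary. The plan names starting size as a possible confounder, fixes no adjustment for it, and proposes a check that misses differences below about 0.64 SD. The 11-13% chance of a difference above 0.5 SD follows from 40 patients and 1:1 allocation alone. It is ordinary chance imbalance and does not show that the randomisation is faulty.

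The gain from about 58% to about 70-85% power rests on assumed values: a 0.7 SD effect, correlations of 0.5 to 0.7, and a t test on follow-up size as the comparator. A weaker correlation, or a t test on change, would make the gain smaller. The benefit of stratified allocation is mainly face validity and protection of outcomes analysed without adjustment.

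**What to change.** **Main change, section VII.**
- Commit, before outcome data are examined, to comparing wound size by ANCOVA with day-0 size as a continuous baseline covariate.
- Include day-0 size in the same way in any comparison of wound closure.
- Delete the baseline significance test and report starting size by arm descriptively.
- State in section V that the post-surgical defect size is measured on day 0.

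This needs no extra patients or visits, because the plan already collects the size; the model spends one degree of freedom.

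**Optional addition, section III.** Measure the defect before the assignment is opened, and allocate from separate prepared permuted-block lists in two size strata, with one cut-off fixed before the first patient. The documents do not give the unit's usual defect size, so the cut-off must come from the unit's own records. The cost is a second list and a fixed order of steps on day 0. The downsides are slightly unequal arm totals if blocks are left incomplete, and the need to keep size in the analysis so that the test does not become conservative.

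### The plan claims double-blinding but does not secure it for patients or for the wound measurements that will be compared

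*Combined protocol and SAP*

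**What the plan says.** Section II sets the aim of testing the device "by way of a double-blinded randomized, controlled study", and the title makes the same claim.

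**Patients.** Section III states that "The patient will remain blinded to the outcome of randomization". The only means described is the sham. On the active light, Section III says "This study will only utilize the 633 nm wavelength". The Introduction gives its colour by comparison: "Similar to the 633 nm light emitted by the LED, red light from the HeNe 633 nm laser". The sham is defined as follows: "In this case, a sham light treatment refers to regular light (not LED) exposure for 20 minutes". Section III adds: "The sham light comes from the same device as the treatment light (Omnilux machine". Each arm has four sessions of 20 minutes at weekly intervals.

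**Outcomes.** Section III says: "Changes from the baseline wound (including length and width) will be measured along with wound depth". It then says that these parameters are compared at the four treatment visits. Weekly follow-up continues until the wound closes or for at most 3 months, with a check one week after closure. The role of the blinded dermatologists is given in one sentence: "The clinical photographs taken before and after either LED or sham light treatment at each study visit will be evaluated by blinded assessor(s".

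**Analysis.** Section VII discusses comparing the groups by t test or ANCOVA and checking wound size at baseline. It does not mention the photograph evaluation.

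**The concern.** A sham protects the comparison only if patients cannot tell it from the active treatment, or cannot see either. Here the active light is red by the protocol's own comparison, and the control light is described only as ordinary light. Patients carry out the daily cleansing and dressing changes themselves (Section V), so a patient who guesses the group could care for the wound differently.

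The second gap matters more. Placing a wound edge, measuring depth and calling a wound closed all involve judgement. The one task that is explicitly blinded, reading photographs, has no stated place in the analysis. The measurements that are to be compared have no stated blinding. If the person measuring knows the arm, expectation can enter the data, and no analysis can remove it afterwards.

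**Working it through.** The plan gives no figure on blinding to reproduce, so the main check compares what is claimed with what is provided.

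| Element | What the text provides | What is missing |
|---|---|---|
| Patient | Stated to be blinded; sham from the same machine (III) | Match of colour, brightness or warmth; shielding of view |
| Person delivering the light | Nothing | Whether blinded, or kept apart from measurement |
| Length, width, depth | Measured and compared at weeks 1 to 4 (III) | Who measures, and whether blinded |
| Closure | Ends follow-up; rechecked one week later (III) | Definition, who decides, and whether blinded |
| Photographs | Evaluated by blinded dermatologists (III) | What is rated, and how it enters the analysis (VII is silent) |

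The group is also among the items recorded for each patient (Section V), and no separation of that record from the people who measure is described.

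**Illustration of what a bias would do.** The size of the bias, *b*, is an assumption; the documents give no value.

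Inputs:
- 40 patients (Section IV.A), two groups randomized in blocks of two (Section III), so 20 per arm.
- Unpaired t test, one of the two options in Section VII, with 20 + 20 − 2 = 38 degrees of freedom.
- Two-sided 5% level (assumed; the plan states none) and no true effect.

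Steps:
1. Standard error of the difference in SD units: √(1/20 + 1/20) = √0.1 = 0.316.
2. Noncentrality: *b* / 0.316, which is 0.632 for *b* = 0.2 and 0.949 for *b* = 0.3.
3. Critical value of t with 38 degrees of freedom: 2.024.
4. False-positive rate: the probability that a noncentral t lies beyond ±2.024.

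| Assumed bias (SD) | Noncentral t | Normal approximation |
|---|---|---|
| 0.1 | 6.1% | 6.2% |
| 0.2 | 9.5% | 9.7% |
| 0.3 | 15.2% | 15.8% |
| 0.5 | 33.8% | 35.3% |

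Normal check at *b* = 0.2: Φ(0.632 − 1.960) + Φ(−0.632 − 1.960) = 0.092 + 0.005 = 0.097.

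The two methods agree closely. The table shows how sensitive a trial of this size is to a modest systematic shift. It is no evidence that such a shift will occur, and a bias against the device would inflate the rate equally.

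**The case against.** The plan does more than use a label. It says that patients are blinded, takes the sham from the same machine and names blinded assessors. Patient plus assessor is one ordinary meaning of double-blind. The camera image carries a measurement stick, so the blinded dermatologists may be meant to read length and width from it. The check one week after closure is a partial safeguard against a false closure call.

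These points stand, and they rule out several stronger readings that a reader might infer:

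- **That patients will be unmasked.** The colour of the ordinary light is not given, nor is what patients are told about the active light. In a parallel-group design each patient sees only one light. A visible difference is a reasonable inference, not a stated fact.
- **That measurement is unblinded and favours the device.** The text does not say who measures or what they know. Follow-up visits after the fourth session involve no light at all. Neither knowledge of the arm nor a direction of bias can be read from the documents.
- **That closure is one of the outcomes compared.** Section III compares change in wound dimensions and depth. Closure appears there as the event that ends follow-up.
- **That photographs taken after the light give the arm away or are useless for judging healing.** The documents describe no visible effect of the light on the skin, and photographs at each visit allow comparison across visits.
- **That a non-LED sham from the same device is a contradiction.** The text does not say that every light source in the machine is an LED. It is an ambiguity to clear up.

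The objection does not close the gap. Image-based reading of length and width by the blinded assessors is possible but not written down, and depth and closure would still be unassigned. Nor does any section say how the sham is matched or hidden.

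**Conclusion.** The point holds in this form: the plan claims double-blinding but does not secure it for patients or for wound measurement. The conclusion rests on what the text assigns and leaves unassigned, and not on any finding that blinding fails. The size of any bias cannot be derived from the documents. The range of about 9.5% to 15% depends wholly on an assumed shift of 0.2 to 0.3 SD, 20 patients per arm and a two-sided 5% t test, and it should not be quoted as an estimate. The change is worth making before enrolment because it is cheap and because bias that enters at measurement cannot be repaired in the analysis.

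**What to change.** 1. Fit identical opaque eyewear in both arms before the device is switched on.
2. At each treatment visit, take the images and measurements used for outcomes before the light session.
3. Have the dermatologist assessor(s) already planned derive length and width, and judge closure, from coded pre-light images read in random order. Images from the later follow-up visits can be coded in the same way.
4. Have depth, and any closure call made at the visit, recorded by existing staff who do not deliver the light and do not know the allocation. Recording depth before looking up the group is not enough: from the second session on, anyone who delivered the first already knows the arm.
5. State who is blinded, and explain how a sham described as not LED comes from the same device. Eyewear does not hide warmth, so the description should say how the two lights compare in that respect too.

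**Cost.** Eyewear, image coding, a reordered visit, a separation of tasks among existing staff and some extra reading time for the assessors. Sample size, treatment and visit schedule are unchanged.
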